### Cohort analysis

To identify differences in clinical course (Primary objective 2) and differences in risk factors (Secondary objective 1) for vaccine associated myocarditis/pericarditis and vaccine unrelated myocarditis/pericarditis, cases in the cohort analysis will be compared based on vaccination status. Outcomes and identified follow-up care will also be characterized, where feasible. If sequelae or unusually severe cases are identified, cases with and without sequelae will be compared.

Standard descriptive statistics (see [Section 9.7](#)) will be used to characterise clinical course, outcomes, and long-term outcomes following the initial myocarditis/pericarditis episode. Cox regression analysis will be utilized to compare the presence of sequelae following myocarditis/pericarditis (e.g., death, subsequent cardiovascular events, cardiac hospitalizations) between recent Moderna vaccination targeting SARS-CoV-2-exposed and unexposed cases as feasible.

If myocarditis and pericarditis cases with severe presentation or long-term sequelae are identified, a similar modelling approach for the cohort design will be applied to explore applicable risk factors as feasible (Secondary objective 2). Candidate risk factors will be selected using a two-step variable selection method: starting with a univariate approach for the selection of relevant variables, and followed by a stepwise backward variable selection approach.

The analysis will be performed per DAP (i.e., models will be trained locally for each DAP), and results will be presented on DAP level. The parameter estimate, SE, and hazard ratio (HR) for each model parameter will be presented together with its 95% CI.

Further details on all analyses can be found in the SAP.

### 9.7.3 Subgroup analyses

Descriptive statistics will be presented for the subgroups as defined in [Section 9.3.4](#). Statistical analyses on subgroups will be considered only if feasible based on available sample size.

### 9.7.4 Missing data

Because of the type of data, missing data are expected to occur due to e.g., the nature of the medical information collected/the source of the data, the amount of data collected and the heterogeneity of databases used.

It is not always possible to differentiate absence from missingness in routinely collected databases. However, the following steps are considered when missingness can be established.

Missingness will first be investigated by presenting an overview of the relevant variables and the frequency and percentage of missing data thereof.

In case the missingness is very limited (<5% for each DAP), a complete-case analysis will be performed.

In case of a larger missingness rate, using a complete-case analysis may introduce bias but also limit the number of cases for inclusion in the prediction model. Considering its informative role in health databases, missing data will be taken into account as a separate category. This will be further specified in the SAP.

### 9.7.5 Sensitivity analyses

Sensitivity analysis will focus on the robustness of results regarding assumptions of the study design, outcome definitions, assumed period of risk, and availability of key data elements and may include the following (as feasible based on available sample size within the applicable subgroups):

- The exposure window for recent exposure to Moderna vaccination targeting SARS-CoV-2 prior to myocarditis/pericarditis events will be shortened from 30 days to 7 days and 14 days.
- The myocarditis/pericarditis case definition may be modified to include (1) validated cases classified as Definitive or Probable (Level 1-2) for a restricted sensitivity analysis, or classified as Definitive, Probable, Possible, or Insufficient Information (Levels 1-4) for an expanded sensitivity analysis, by adjudication criteria according to the Brighton Collaboration Case Definition, or (2) all cases (including validated and unvalidated cases) .
- If a large number of individuals with a history of myocarditis/pericarditis are identified, these individuals may be excluded in sensitivity analyses.

### **9.7.6 Other analyses**

Separate analyses for different Moderna vaccine products targeting SARS-CoV-2, for example, elasomeran, elasomeran/imelasomeran, elasomeran/davesomeran, will be performed as feasible for those DAPs that have data on different products available. For each vaccine variant, descriptive analyses will be presented. Both the case-cohort as the cohort analyses will be performed separately for the vaccine variants if the sample size for both vaccines is sufficiently large.

### **9.8 Quality control**

The source, electronic routinely collected data, proposed for use in this study will undergo standard curation and quality-check procedures and curation by the data custodians. Standard operating procedures or internal process guidance at each research centre will be adhered to for the conduct of the study. These procedures will include internal quality audits, rules for secure and confidential data storage, methods to maintain and archive project documents, quality-control procedures for programming, and standards for writing analysis plans. Routine procedures will include checking electronic files, maintaining security and data confidentiality, following analysis plans, and performing quality-control checks of all programs. Each partner should maintain any patient-identifying information securely on site according to internal standard operating procedures or guidance documents.

This study will be conducted in accordance with the Guideline on good pharmacovigilance practices (GVP), including the European Network of Centres for Pharmacoepidemiology and Pharmacovigilance (ENCePP) Code of Conduct.

### **9.9 Limitations of the research methods**

With the use of large secondary administrative databases in general, it remains difficult to ascertain the details of myocarditis and pericarditis events and other high-resolution data. In addition, while including administrative databases from different countries increases generalizability and size of the overall dataset, it also introduces heterogeneity in data collection methods, data quality, availability of variables and relations between variables. It is recognized that especially the availability and collection of lifestyle factors will be a limiting factor on the risk factor data inclusion in the proposed analyses for both the case-cohort and cohort studies. These concerns are tackled as best as possible by using all the implemented infrastructure of VAC4EU including the well-defined CDM and quality control procedures executed at various stages. In addition, a case validation is performed to verify that cases are true cases, based on criteria from the Brighton Collaboration. Furthermore, heterogeneity between DAPs will be investigated by performing specified analyses both at a local level and overall, as feasible.

Despite the large size of the underlying populations, the size of the Moderna vaccination targeting SARS-CoV-2- exposed cohort that develop myocarditis/pericarditis is relatively small, and validation of cases may further reduce the number of cases included in analyses. This could limit the amount of risk factors and prognostic factors that can be investigated in the case-cohort design

and might make some (subgroup) analyses challenging regarding achieving adequately powered statistical analyses. Data availability may also limit our ability to address primary and secondary study objectives related to the identification of lifestyle factors as risk factors for the development of myocarditis/pericarditis. While the merits of investigating lifestyle factors as potential risk factors may be questioned when the data availability cannot be assured, we believe it is central to the research question to consider and rule out potential confounders whenever possible. Namely, we want to be able to determine the risk of myocarditis or pericarditis following vaccinations targeting SARS-CoV-2 over and above other common factors (e.g., age, smoking status). To this end, we will investigate as many lifestyle factors as feasible across all DAPs. Where not feasible (i.e., certain DAPs are missing a given lifestyle factor), analyses will include a smaller subset of variables and/or will only be done for those DAPs that have the requisite data available.

The sampling of cases (i.e., myocarditis or pericarditis not following vaccination) to be validated could pose a limitation in the characterization of the clinical course of cases not following vaccination. As most myocarditis and pericarditis cases following vaccination are expected to occur in young adults, age-matched non-vaccine related myocarditis/pericarditis cases will also mainly comprise of young adults. This may lead to an underrepresentation of non-vaccination related cases in older individuals in the cohort analysis. However, the sensitivity analysis including all cases, regardless of being validated or not, will provide information regarding the clinical course of non-vaccine related cases in possible underrepresented age groups.

There are a few other potential validity issues in this study. Selection bias is not expected to pose a threat to validity, as the routinely collected data are sufficiently representative of the background population. That is, the registries have full population coverage in Denmark and Norway, while the regional databases in Spain are representative with respect to background rates and demographic distributions of the underlying populations. Similarly, the CPRD is broadly representative of the UK population (see [Annex 3](#)).

Information bias may cause a threat in classification of the outcomes (myocarditis/pericarditis), in both the case-cohort and cohort studies. As became more well-known among the general public that myocardial side effects may occur after vaccinations targeting SARS-CoV-2 with young males most at risk, the chances of diagnosis among young males may have become higher compared to other groups. This could be due to young males' increased vigilance and a corresponding increase in their likelihood to report symptoms following vaccination. Alternatively or in conjunction, the well-documented nocebo effectError! Reference source not found.,Error! Reference source not found.,Error! Reference source not found. suggests increased knowledge and negative expectations of a given side effect can render its occurrence more likely. While beyond the scope of the current studies to determine the rate of information bias in the case-cohort and cohort samples, it is worth noting its occurrence may contribute to variance in observed myocarditis/pericarditis among certain subsamples (namely young males). Our inability to disentangle the rate of nocebo vaccine-related myocarditis constitutes a limitation, recognized and seen as not insignificant by other COVID-19 researchers.

Conducting retrospective analyses on observational data, we will attempt to adjust for potential confounders in both the case-cohort and cohort studies. Namely, we will perform multivariable analyses as feasible, examining the effect of predictors of interest over and above potential confounders. Moreover, we will attempt to control for the effects of lifestyle variables as much as statistically possible and feasible by including them as covariables into the multivariable model.

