**Population:**

For the case-cohort design, the cohort is the group of individuals with at least one dose of a Moderna vaccination targeting SARS-CoV-2. Inclusion criteria are at least one year of enrolment in the applicable database prior to the index vaccine dose and without myocarditis events within 6 months prior to receiving a Moderna vaccination targeting SARS-CoV-2. Cases are individuals meeting the criteria of myocarditis or pericarditis. Moreover, cases should be able to meet the adjudication criteria according to the Brighton Collaboration Case Definition for possible, probable, or definite myocarditis or pericarditis.

For the cohort design, individuals meeting the criteria of myocarditis or pericarditis, with at least one year of enrolment in the applicable database prior to the index myocarditis or pericarditis event will be included. Cases of myocarditis and pericarditis will be excluded if these individuals have no record of a Moderna vaccine targeting SARS-CoV-2 but a record of another vaccine targeting SARS-CoV-2 within 30 days prior to the onset of myocarditis or pericarditis. Within the cohort design, all cases following vaccination are adjudicated according to the Brighton Collaboration Case Definition. A 1:1 matched sample of the cases not following vaccination matched based on sex and age will also be adjudicated. Only cases that meet the adjudication criteria for possible, probable, or definite myocarditis or pericarditis are included.

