On 09 July 2021, the EMA's Pharmacovigilance Risk Assessment Committee (PRAC) concluded that myocarditis can occur in very rare cases following vaccination with the two current mRNA vaccines targeting SARS-CoV-2. This conclusion was reached after an in-depth review of 145 cases of myocarditis in the European Economic Area (EEA) among people who received Comirnaty and 19 cases among people who received the Moderna vaccine. PRAC also reviewed reports of 138 cases of pericarditis following the use of Comirnaty and 19 cases following the use of the Moderna vaccine. The PRAC concluded that the cases primarily occurred within 14 days after vaccination, more frequently after the second dose, with young age, and male sex identified as potential risk factor for occurrence. Among those with myocarditis, advanced age and concomitant diseases were risk factors for subsequent mortality. As PRAC qualified this adverse event of special interest (AESI) as 'very rare', an updated product information will list myocarditis as side effects with very rare frequency and health care professionals are advised that the cases may need specialist care. Although vaccine trials are usually large, they may not detect rare adverse events. In addition, there is a high safety standard applied to a preventive agent administered to individuals in their usual state of health.

Population-based descriptive studies have addressed the occurrence of myocarditis after mRNA-based vaccination targeting SARS-CoV-2. In Denmark, 21 persons among a half million individuals who received the Moderna vaccination targeting SARS-CoV-2 developed myopericarditis within 28 days from vaccination date. The Moderna vaccination targeting SARS-CoV-2 was associated with a significantly increased risk compared to unvaccinated individuals. In another study passive surveillance reporting in the US showed that rates of myocarditis were highest after the second

vaccination dose of mRNA-based vaccines. In the latter study 490 myocarditis cases following Moderna vaccination targeting SARS-CoV-2 were reported to the Vaccine Adverse Event Reporting System. As both studies merely focused on short-term follow-up and myocarditis is a rare adverse event, larger international studies with longer follow-up time are needed.

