### **8.1 Primary objectives**

1. To identify possible risk factors for myocarditis and pericarditis following Moderna vaccination targeting SARS-CoV-2, including demographic characteristics, medical history, and vaccination characteristics.
2. To characterize the clinical course of myocarditis and pericarditis of varying origin, including myocarditis and pericarditis associated with Moderna vaccination targeting SARS-CoV-2, and myocarditis or pericarditis not associated with vaccinations targeting SARS-CoV-2, and to identify prognostic factors in the course of myocarditis and pericarditis

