## **9. Research methods**

### **9.1 Study design**

To answer the objectives, this study will use an Moderna vaccination targeting SARS-CoV-2-exposed case-cohort design and a myocarditis cohort study design (Figure 1).

The case-cohort design will be used to assess risk factors other than Moderna vaccination targeting SARS-CoV-2 for the development of myocarditis and pericarditis in recipients of the Moderna vaccine targeting SARS-CoV-2, to understand which characteristics increase or decrease the risk for the development of myocarditis and pericarditis after vaccination (i.e., t0). This may contribute to risk assessment and identification of individuals who do not have an increased risk on myocarditis or pericarditis.

[figure not shown]
The cohort design will be used to describe prognostic factors for a (severe) clinical course in patients with myocarditis or pericarditis regardless of vaccination status. As most myocarditis and pericarditis cases are mild in disease severity, it is clinically relevant to identify the individuals who are at increased risk for severe clinical outcomes as early as possible, in order to provide appropriate care in a timely manner. These severe outcomes are acute coronary syndrome, acute myocardial infarction, heart failure, atrial fibrillation/flutter, ventricular arrhythmias/cardiac arrest, pulmonary embolism or deep venous thrombosis, stroke outcomes, peripheral arterial embolism, hospital readmission, ICU admission or death. Therefore, information available at the onset of myocarditis or pericarditis (i.e., t1) could be used to predict the clinical course including long-term outcomes (i.e., t2).

The cohort design will also be used to address both secondary study objectives. Within the cohort of myocarditis/pericarditis cases, clinical course and risk profiles will be compared between patients with myocarditis/pericarditis recorded after vaccination targeting SARS-CoV-2 and patients with myocarditis/pericarditis unrelated to vaccine administration. Moreover, risk factors for severe myocarditis/pericarditis will be investigated within this cohort.

Recipients of Moderna vaccination targeting SARS-CoV-2 and cases of myocarditis and pericarditis will be identified between January 2021 (date of the earliest approval of Moderna vaccines targeting SARS-CoV-2 in Europe) and the end of the study period (defined as most recent data availability at the time of the End of Data collection).

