### 9.2.2 Inclusion criteria

For the Moderna vaccination targeting SARS-CoV-2-exposed case-cohort design, a cohort will first be defined including individuals of all ages with (1) at least one dose of Moderna vaccination targeting SARS-CoV-2 administered during the study period, (2) at least one year of enrolment in the applicable database prior to the index vaccine dose to allow for ascertainment of baseline covariables and potential risk factors, and (3) no myocarditis or pericarditis events within 6 months prior to Moderna vaccination receipt. Myocarditis and pericarditis cases are defined when adjudication criteria according to the Brighton Collaboration Case Definition for possible, probable or definite myocarditis or pericarditis is fulfilled. Cases and controls are defined as mentioned in [Section 9.1.1](#).

In the cohort design, all cases following vaccination, and only a sample of cases not following vaccination will undergo adjudication. In the analyses, individuals will be included if they: (1) have been adjudicated and meet the adjudication criteria according to the Brighton Collaboration Case Definition for possible, probable or definite myocarditis or pericarditis, and (2) have at least one year of enrolment in the applicable database prior to the index myocarditis or pericarditis event to allow for ascertainment of baseline covariates and potential risk factors.

For both the case-cohort as the cohort design, individuals with administrative codes for myocarditis or pericarditis will be identified in each data source. Following this initial screening, selected cases will be confirmed based on review of clinical data (based on criteria according to the Brighton Collaboration). The selection will include all cases of myocarditis and pericarditis following Moderna vaccination targeting SARS-CoV-2, as well as an age- and sex- matched sub-sample of other cases.

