### **9.2.3 Exclusion criteria**

Individuals not meeting criteria outlined in [Section 9.2.2](#) are excluded from the Moderna vaccination targeting SARS-CoV-2-exposed case-cohort and myocarditis/pericarditis cohort analyses, respectively. For the cohort design an additional exclusion criterium is applied: Persons with no record of a Moderna vaccine targeting SARS-CoV-2 but record of another vaccine for SARS-CoV-2 within 30 days prior to index date of myocarditis or pericarditis event will be excluded. Individuals who have evidence of myocarditis or pericarditis in structured data (e.g., ICD-10 codes) where review of clinical data is not performed due to sampling, or is incompatible with adjudication criteria according to the Brighton Collaboration Case Definition for myocarditis or pericarditis will be described but will not be included as cases in primary analyses. In the Moderna vaccination targeting SARS-CoV-2-exposed case-cohort design, non-confirmed myocarditis/pericarditis cases will be censored at the onset of the false positive myocarditis/pericarditis diagnosis.

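### The stand-alone description of non-vaccine cases under primary objective 2 refers to the vaccine cases' age and sex mix, and the planned remedy cannot separate age mix from case validity

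*Protocol*

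**What the plan says.** Protocol Section 8.1 sets primary objective 2 as "To characterize the clinical course of myocarditis and pericarditis of varying origin", and names cases not associated with vaccination among those origins. Section 9.1 says that the cohort design will describe "prognostic factors for a (severe) clinical course in patients with myocarditis or pericarditis regardless of vaccination status".

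The cohort's analysis set is narrower. Under Section 9.2.2 all post-vaccination cases are adjudicated, but "only a sample of cases not following vaccination will undergo adjudication". The abstract (Population) gives the sampling rule: "A 1:1 matched sample of the cases not following vaccination matched based on sex and age will also be adjudicated". Section 9.2.3 says that coded cases left unreviewed because of sampling "will be described but will not be included as cases in primary analyses".

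For the estimator, Section 9.7.2 (Cohort analysis) says that standard descriptive statistics "will be used to characterise clinical course, outcomes, and long-term outcomes following the initial myocarditis/pericarditis episode". It names no weighting or standardisation. The same section attaches the comparison of clinical course by vaccination status to primary objective 2 as well.

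Section 9.9 acknowledges the effect of sampling: "This may lead to an underrepresentation of non-vaccination related cases in older individuals in the cohort analysis". It answers that the sensitivity analysis on all cases, validated or not, will inform on under-represented ages. Section 9.7.5 lists that analysis among items that may be included, as feasible.

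**The concern.** Matching non-vaccine cases to vaccine cases on age and sex is sound for comparing the two groups. It is less suited to describing non-vaccine disease in its own right, which primary objective 2 also asks for. The sampled group takes on the vaccine cases' age and sex mix, and Section 9.9 expects those cases to be mainly young adults. A table headed as non-vaccine myocarditis would in fact show non-vaccine myocarditis in that mix.

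This matters if the course of disease varies with age. Section 7 reports that, among those with myocarditis, "advanced age and concomitant diseases were risk factors for subsequent mortality". If older cases also do worse on the other outcomes, the severity of non-vaccine disease would be understated.

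The stated remedy is weak in two ways. One section treats it as certain and another as optional. It also pools validated with unvalidated cases, so a reader could not tell whether a changed result came from the older ages or from false-positive diagnoses. Section 9.9 also says that selection bias is not expected, because the source databases are representative. That argument concerns the databases and does not cover the selection made by the adjudication sample.

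**Working it through.** **1. Size of the sample, from the protocol's own figures.** Section 9.5 expects 20–80 myocarditis and 50–140 pericarditis cases per DAP in the case-cohort. With 1:1 sampling, the cohort is twice that:

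- myocarditis: 2 × 20 = 40 to 2 × 80 = 160
- pericarditis: 2 × 50 = 100 to 2 × 140 = 280

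These reproduce the stated cohort sizes of 40–160 and 100–280, read as per-DAP figures. The abstract labels them per DAP; Section 9.5 gives them without that label. On this reading, about 20–80 non-vaccine myocarditis and 50–140 non-vaccine pericarditis cases per DAP are sampled, in the vaccine cases' age and sex mix.

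**2. Unweighted against weighted share.** The documents give no age mix and no outcome rates, so the following inputs are assumptions for illustration:

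- *v*, share of young cases among vaccine cases, and so in the matched sample: 60–80%
- *c*, share of young cases among all non-vaccine cases: 30–50%
- severe-outcome risk: 5% in young cases, 10–20% in older cases

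Unweighted share = *v* × r(young) + (1 − *v*) × r(older). Weighted share = *c* × r(young) + (1 − *c*) × r(older).

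| v | c | r(young) | r(older) | Unweighted | Weighted | Ratio |
|---|---|---|---|---|---|---|
| 0.8 | 0.3 | 5% | 20% | 4.0 + 4.0 = 8.0% | 1.5 + 14.0 = 15.5% | 0.52 |
| 0.7 | 0.3 | 5% | 20% | 3.5 + 6.0 = 9.5% | 1.5 + 14.0 = 15.5% | 0.61 |
| 0.6 | 0.5 | 5% | 10% | 3.0 + 4.0 = 7.0% | 2.5 + 5.0 = 7.5% | 0.93 |
| any | any | 5% | 5% | 5.0% | 5.0% | 1.00 |
| 0.6 | 0.5 | 5% | 3% | 3.0 + 1.2 = 4.2% | 2.5 + 1.5 = 4.0% | 1.05 |
| 0.8 | 0.3 | 5% | 3% | 4.0 + 0.6 = 4.6% | 1.5 + 2.1 = 3.6% | 1.28 |

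The ratio runs from 0.52 to 0.93 when older cases do worse. It is 1 when risk does not vary with age or the two age mixes agree, and above 1 when older risk is lower.

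**3. Cost in precision.** With two age strata, the Kish design effect is *c*²/*v* + (1 − *c*)²/(1 − *v*).

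- *v* = 0.6, *c* = 0.5: 0.25/0.6 + 0.25/0.4 = 1.04
- *v* = 0.8, *c* = 0.3: 0.09/0.8 + 0.49/0.2 = 2.56

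At 2.56, 20–80 sampled cases act as 20/2.56 = 8 to 80/2.56 = 31. Only 0.2 × 20 = 4 to 0.2 × 80 = 16 older cases per DAP would then carry 70% of the estimate. In the middle scenario (*v* = 0.7, *c* = 0.3, risks 5% and 20%) with 80 sampled cases, the 95% half-width is 6.4 points unweighted and 11.3 points weighted.

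**4. Can the weights be formed?** Section 9.2.2 identifies all coded cases in each data source before the sample is drawn. Coded and sampled counts by age, sex and diagnosis can therefore be derived, although the protocol does not state them.

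**The case against.** The strongest reply is that the protocol nowhere says the description will be unweighted. Section 9.7 leaves full analysis details to the SAP, which was not available for this review, and weights are ordinary SAP content. That stands: a reader might infer that the sponsor has decided against weighting, and the text does not support this. What remains is what the protocol itself fixes: the sampling rule, the analysis set and a stated remedy that does not isolate the age effect.

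A reader might also infer that the whole of primary objective 2 is compromised. It is not. Section 9.7.2 assigns the contrast by vaccination status to that objective, and matching serves the contrast well. Only the stand-alone description of non-vaccine cases is affected.

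Nor does this sampling by itself bias the prognostic models. Selection is on age and sex, both measured covariables, and not on outcome. A correctly specified model that includes them still estimates the conditional hazard ratios, with less information at older ages.

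The limitation is disclosed, and the all-case analysis is not the only response, since Section 9.2.3 also has unsampled cases described. That helps little, because those cases are unvalidated.

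Finally, weighting is fragile with so few older cases per DAP. Merging age bands to fill empty cells would let younger sampled cases stand in for older unsampled ones, which restores the distortion. This objection is right and shapes the fix.

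**Conclusion.** The point holds as a cheap improvement to one part of primary objective 2. The description of non-vaccine cases as a group will refer to the vaccine cases' age and sex mix. Section 9.9 concedes the under-representation, and its main remedy is optional elsewhere and confounds age mix with case validity.

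The size is not known. Under the assumed inputs the unweighted severe share is about 0.52 to 0.93 of the weighted share. A reader might conclude that non-vaccine disease is made to look milder; the documents do not establish this. They give no age mix and no severity rates, and the only support for direction, in Section 7, concerns mortality, whereas the composite also counts events such as readmission and ICU admission. The direction depends on older cases doing worse and on non-vaccine cases being older than vaccine cases.

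**What to change.** - Keep the unweighted matched set for every vaccine versus non-vaccine comparison, including the clinical-course contrast that Section 9.7.2 places under primary objective 2, and for the models adjusted for age and sex.
- For the stand-alone description of adjudicated non-vaccine cases, add results by age band.
- Add a weighted version: within each DAP, weight each case by coded divided by sampled counts in broad age-sex-diagnosis cells, with robust standard errors. Limit the target to age ranges that contain sampled cases, state that range, and do not merge bands to cover empty ones.
- Label the unweighted description as referring to the vaccine cases' age and sex mix.
- Reconcile Section 9.7.5 with Section 9.9 so that the all-case analysis is firmly planned.

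The cost is some SAP and protocol wording, one weight variable and a few tables, with no additional chart review. The downside is precision: intervals widen, and with few older sampled cases per DAP the weighted estimates may be unstable. They should therefore be supplementary and read beside the age-band results.
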